#### 6.5.4.5 Immune Cell-Associated Neurotoxicity Syndrome (ICANS)

Immune cell-associated neurotoxicity syndrome (ICANS) is a neuropsychiatric syndrome which is frequently associated with CRS; however, it is specifically excluded from the definition of CRS and can occur during the course of CRS, after its resolution, or independently from CRS. Clinical findings can be progressive and may include aphasia, altered level of consciousness, impairment of cognitive skills, motor weakness, seizure, and cerebral edema. Severity is evaluated using the

ASTCT Consensus grading scale, with ICE score for encephalopathy assessment (Section 10.13 of the master protocol). Recommendations for ICANS management mainly include the use of steroids, whereas tocilizumab or alternative therapies per site practice in CRS management should only be used in the context of CRS, as outlined in Table 6. The proposed management should be considered only as recommendations and in light of recommendations from site specialist.

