#### 6.5.4.3 Fever, flu-like symptoms and cytokine-release syndrome (CRS)

Fever can frequently happen with infusion of IL-2 and may possibly evolve into flu-like symptoms or could be an early manifestation of CRS. Fever or flu-like symptoms should be graded according to CTCAE V5.0 and managed according to institutional standards.

Monitoring of vital signs is detailed in Safety Assessments (Section 8.2.2).

Cytokine-release syndrome should be graded as per American Society for Transplantation and Cellular Therapy (ASTCT) criteria integrated with central laboratory cytokine results, and managed per guidelines in Table 4. If any grade of CRS is suspected, sites should make every effort to draw an additional blood sample for cytokines levels (by central laboratory) prior to the administration of tocilizumab or alternative therapies per site practice in CRS management, as well as C-reactive protein (CRP) and ferritin (by local laboratory).

Sites should have at least 2 full doses of tocilizumab or alternative therapies per site practice in CRS management available and access to an intensive care unit (ICU), in case participants develop CRS.

Guidelines for management of CRS according to severity grading are provided in [Table 4](#).  
ASTCT CRS consensus grading scale is provided in Section 10.13 of the master protocol.

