|  | 
If no clinical improvement in oxygenation, hypotension, fever, and other CRS manifestations is observed within 24 to 72 hours, initiate management for persistent or worsening CRS. Re-evaluation for other contributing conditions will be done, such as infection, cardiac, thromboembolic and other complications. Intravenous Tocilizumab at 8 mg/kg (for participants weighing <math>\geq 30</math> kg) or alternative therapies per site practice in CRS management should be administered, and steroids should be administered concurrently. If still no improvement in oxygenation, hypotension fever and other manifestations is observed after the first dose of tocilizumab, it may be repeated after an interval of at least 8 hours and should not exceed 4 doses in total.
 
For participants with severe CRS who fail to improve after repetitive treatment with both tocilizumab or alternative therapies per site practice in CRS management and steroids, alternative options will be discussed with clinical site specialists
 |

- a Information for preparation and storage of SAR444245 is provided in the pharmacy manual.
- b Fever is defined as temperature  $\geq 38^{\circ}\text{C}$  not attributable to any other cause. In patients who have CRS then receive antipyretic or anticytokine therapy such as tocilizumab or alternative therapies per site practice in CRS management or steroids, fever is no longer required to grade subsequent CRS severity. In this case, CRS grading is driven by hypotension and/or hypoxia.
- c CRS grade is determined by the more severe event: hypotension or hypoxia not attributable to any other cause. For example, a patient with temperature of  $39.5^{\circ}\text{C}$ , hypotension requiring 1 vasopressor, and hypoxia requiring low-flow nasal cannula is classified as Grade 3 CRS.
- d Low-flow nasal cannula is defined as oxygen delivered at  $\leq 6$  L/minute. Low flow also includes blow-by oxygen delivery, sometimes used in pediatrics. High-flow nasal cannula is defined as oxygen delivered at  $>6$  L/minute.

Abbreviations: AE = Adverse event; ASTCT=American Society for Transplantation and Cellular Therapy; BiPAP= Bilevel Positive Airway Pressure; CPAP= Continuous Positive Airway Pressure; CRS= cytokine release syndrome; ICU=intensive care unit; IL = Interleukin; IMP=investigational medicinal product; IV = Intravenous; NSAIDs=Non-steroidal anti-inflammatory drugs.

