| Severe or Life-threatening
Grade 3
ICE score 0-2. Awakens only to tactile stimulus.
Any clinical seizure focal or generalized that resolves rapidly or nonconvulsive seizures on EEG that resolve with intervention.
Grade 4
ICE score: 0 (participant is unarousable and unable to perform ICE).
Participant is unarousable or requires vigorous or repetitive tactile stimuli to arouse. Stupor or coma.
Life-threatening prolonged seizure (>5 min); or Repetitive clinical or electrical seizures without return to baseline in between.
Deep focal motor weakness such as hemiparesis or paraparesis.
Diffuse cerebral edema on neuroimaging; decerebrate or decorticate posturing; or cranial nerve VI palsy; or papilledema; or Cushing's triad. | If Grade 3 ICANS, delay SAR444245.
When symptoms have resolved or improved to Grade 1 after corticosteroid taper, SAR444245 can be either restarted at ■ μg/kg or permanently discontinued, as clinically indicated, and upon discussions between the Investigator and Sponsor.
Treatment with IV corticosteroids should be initiated. Concomitant CRS may require tocilizumab or alternative therapies per site practice in CRS management and should be handled as described in Section 6.5.4.3.
Corticosteroids can then be administered IV or orally every 8 hours for up to 3 days, then tapered over 4 days.

If Grade 4 ICANS, permanently discontinue SAR444245.
Treatment with IV corticosteroids should be initiated. Concomitant CRS may require tocilizumab or alternative therapies per site practice in CRS management and should be handled as described in Section 6.5.4.3.
Corticosteroids can then be administered IV or orally every 8 hours for up to 3 days, then tapered over 4 days.

For both Grade 3 and Grade 4 ICANS
If there is no clinical improvement within 24 to 72 hours, then re-evaluation for other contributing conditions should be done. Administration of IV Tocilizumab at 8 mg/kg (for participants weighing ≥30 kg, total dose should not exceed 800 mg) or alternative therapies per site practice in CRS management should be considered, and steroids should be administered concurrently and repeated as previously mentioned for CRS. Neurologist and other relevant clinical specialists should be involved whenever indicated. |

a Information for preparation and storage of SAR444245 is provided in the pharmacy manual  

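### Substudy 01 gives tocilizumab 8 mg/kg in both Table 4 (CRS) and Table 6 (ICANS), but only Table 6 sets an 800 mg limit

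*Protocol*

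**What the plan says.** **Dose.** In Substudy 01, Table 6, the paragraph covering Grade 3 and Grade 4 ICANS together gives the dose and its limit: "Administration of IV Tocilizumab at 8 mg/kg (for participants weighing ≥30 kg, total dose should not exceed 800 mg". In Table 4, for CRS that has not improved within 24 to 72 hours, tocilizumab is also given intravenously at 8 mg/kg with the same 30 kg weight threshold. The text runs straight on from the dose: "or alternative therapies per site practice in CRS management should be administered, and steroids should be administered concurrently". No limit in mg appears. The limits that Table 4 does set concern repetition: "it may be repeated after an interval of at least 8 hours and should not exceed 4 doses in total".

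**Link between the tables.** The separate Grade 3 and Grade 4 paragraphs of Table 6 both say: "Concomitant CRS may require tocilizumab or alternative therapies per site practice in CRS management and should be handled as described in Section 6.5.4.3". Section 6.5.4.3 in turn says that CRS is to be "managed per guidelines in Table 4".

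**CRS condition.** Section 6.5.4.5, which introduces Table 6, says that "tocilizumab or alternative therapies per site practice in CRS management should only be used in the context of CRS" and points to Table 6 for the details. It also says that ICANS "can occur during the course of CRS, after its resolution, or independently from CRS". The joint Grade 3/4 paragraph of Table 6 opens with "If there is no clinical improvement within 24 to 72 hours, then re-evaluation for other contributing conditions should be done" and then says that tocilizumab or an alternative should be considered. It does not state the CRS condition.

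**Status of the guidance.** Section 6.5.4.5 describes the ICANS management as recommendations, to be read with the advice of the site specialist. Section 6.5.3 leaves the final decision on corrective therapy to the Investigator.

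**The concern.** The same drug, at the same mg/kg dose and with the same weight threshold, carries a maximum in one table and none in the other. A site treating CRS would open Table 4 and find no reason to stop at 800 mg. For a participant with CRS and ICANS together the two tables apply at once and can give different doses. That overlap is realistic: the master protocol's risk table describes one first-in-human participant, on 24 µg/kg monotherapy, with Grade 4 CRS and neurological symptoms who was treated with tocilizumab and a steroid. Weight is not an eligibility criterion in the master protocol, so heavy participants can enrol.

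The wording of the CRS condition matters less, but it concerns severe events. Section 6.5.4.5 foresees ICANS without CRS, and for that situation the joint paragraph of Table 6, read by itself, could be taken to suggest something that the section text restricts. The master protocol (6.8.2) prohibits anti-IL6 therapy apart from stated exceptions, and for ICANS it refers to Section 6.5 of the substudy. The wording therefore has to be settled in the substudy.

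**Working it through.** The plan states no figure for this point that could be reproduced. The check compares the texts and then finds the weight at which the two tables part.

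**Inputs**

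| Item | Table 4 (CRS) | Table 6 (ICANS, joint Grade 3/4 paragraph) |
|---|---|---|
| Dose | 8 mg/kg IV | 8 mg/kg IV |
| Weight threshold | at least 30 kg | at least 30 kg |
| Limit in mg | none stated | 800 mg |
| Repetition | at least 8 hours apart, at most 4 doses | refers back to the CRS scheme |
| Strength of advice | should be administered | should be considered |

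**Step 1: does one participant fall under both tables?** Yes, if ICANS and CRS occur together. Table 6 sends concomitant CRS to Section 6.5.4.3, which sends it to Table 4. A participant with CRS alone is under Table 4 only.

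**Step 2: where do the doses differ?** Table 6 does not say whether its limit is per infusion or over all infusions. Per infusion is assumed.
- Threshold weight = limit / dose per kg = 800 / 8 = 100 kg.
- Up to 100 kg, 8 mg/kg is at most 800 mg, so the tables give the same dose.
- Above 100 kg, Table 4 as written gives more than the Table 6 maximum.

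**Step 3: size above the threshold.** For an illustrative weight of 120 kg:
- Table 4: 8 × 120 = 960 mg.
- Table 6: 800 mg.
- Difference: 960 − 800 = 160 mg, and 960 / 800 = 1.20, so 20% more per infusion.
- Over the four doses that Table 4 permits: 4 × 960 = 3840 mg against 4 × 800 = 3200 mg.

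The protocol gives no weight distribution, so the number of participants above 100 kg cannot be estimated. Cohort A1 is planned at approximately 40 participants in total.

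**Step 4: the CRS condition.** Section 6.5.4.5 states it. The separate Grade 3 and Grade 4 paragraphs of Table 6 reflect it, because they tie tocilizumab to concomitant CRS. The joint paragraph that follows does not mention it; its trigger is lack of improvement within 24 to 72 hours.

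**The case against.** **On the dose.** Table 4 covers CRS and Table 6 covers ICANS, so a participant with CRS alone and above 100 kg is not subject to the Table 6 limit. Calling that case a breach would be wrong. Even where both events occur, giving 800 mg satisfies Table 6 and exceeds nothing in Table 4. Sites may also use alternatives to tocilizumab. All of this stands, and it narrows the direct overlap to participants above 100 kg with both events. It does not explain why the same mg/kg dose has a maximum in one table and none in the other, and Table 4 followed as written still exceeds the only maximum that the substudy states.

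**A stronger reading of the limit.** A reader might infer that the 800 mg covers all infusions together. Four doses would then exceed it at every weight covered (4 × 8 × 30 = 960 mg at 30 kg). The documents do not support this: it would defeat the four-dose allowance in Table 4, to which Table 6 itself refers back.

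**A stronger reading of the CRS condition.** A reader might also infer that Section 6.5.4.5 and Table 6 give opposite instructions for ICANS without CRS. The documents do not go that far. The section text governs the table, and the joint paragraph keeps to CRS terms when it names alternative therapies and repetition. Read under the CRS condition, that paragraph still adds a time trigger, a re-evaluation, a dose, concurrent steroids and specialist involvement, so it is not redundant. What remains is a condition not repeated in one paragraph.

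**Conclusion.** The dose inconsistency holds. On the per-infusion reading, the tables agree up to 100 kg and differ above it, by 160 mg or 20% in the 120 kg illustration. For a participant with both CRS and ICANS above that weight, two different doses apply; for CRS alone, the missing limit is an inconsistency and not a direct conflict.

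The missing CRS condition in the joint Grade 3/4 paragraph of Table 6 is a minor wording point. Which text should change is a clinical choice.

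Both points concern advisory safety guidance, and few participants are likely to be affected. The objective response rate analysis, the analysis populations and the sample size are unaffected. The check covers Substudy 01 only, because the corresponding sections of Substudy 02 are not shown. None of the relevant wording is redacted.

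**What to change.** In Substudy 01, write *8 mg/kg, not exceeding 800 mg per infusion* in both Table 4 and Table 6, keeping the 30 kg threshold. This also settles what the limit refers to. The sponsor should first confirm that per infusion is what it intends.

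Then align Section 6.5.4.5 with the joint Grade 3/4 paragraph of Table 6. If tocilizumab is meant only for ICANS with CRS, add that condition to the paragraph. If rescue use without CRS is intended, amend the sentence in Section 6.5.4.5 instead.

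The cost is a few words in the next amendment. No participants, visits or procedures are added.

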**Table 6 - Guidelines for the management of immune Cell-Associated Neurotoxicity Syndrome (ICANS)**

| Event severity
(ASTCT Consensus Grading criteria)  | Recommended SAR444245
dose modification and supportive care guidelines   |
|---|---|
| Mild
Grade 1
ICE score 7-9. Awakens spontaneously  | No intervention required other than close clinical monitoring.  |
| Moderate
Grade 2
ICE score 3-6. Awakens to voice.  | Delay SAR444245a.
Initiate treatment with IV corticosteroids as needed.
SAR444245 may be resumed only after participant recovery or improvement to Grade 1 after corticosteroid taper. Consideration for reduction of SAR444245 dose to ■ μg/kg as per Investigator with Sponsor consultation.  |
| Severe or Life-threatening
Grade 3
ICE score 0-2. Awakens only to tactile stimulus.
Any clinical seizure focal or generalized that resolves rapidly or nonconvulsive seizures on EEG that resolve with intervention.
Grade 4
ICE score: 0 (participant is unarousable and unable to perform ICE).
Participant is unarousable or requires vigorous or repetitive tactile stimuli to arouse. Stupor or coma.
Life-threatening prolonged seizure (>5 min); or Repetitive clinical or electrical seizures without return to baseline in between.
Deep focal motor weakness such as hemiparesis or paraparesis.
Diffuse cerebral edema on neuroimaging; decerebrate or decorticate posturing; or cranial nerve VI palsy; or papilledema; or Cushing's triad. | If Grade 3 ICANS, delay SAR444245.
When symptoms have resolved or improved to Grade 1 after corticosteroid taper, SAR444245 can be either restarted at ■ μg/kg or permanently discontinued, as clinically indicated, and upon discussions between the Investigator and Sponsor.
Treatment with IV corticosteroids should be initiated. Concomitant CRS may require tocilizumab or alternative therapies per site practice in CRS management and should be handled as described in Section 6.5.4.3.
Corticosteroids can then be administered IV or orally every 8 hours for up to 3 days, then tapered over 4 days.

If Grade 4 ICANS, permanently discontinue SAR444245.
Treatment with IV corticosteroids should be initiated. Concomitant CRS may require tocilizumab or alternative therapies per site practice in CRS management and should be handled as described in Section 6.5.4.3.
Corticosteroids can then be administered IV or orally every 8 hours for up to 3 days, then tapered over 4 days.

For both Grade 3 and Grade 4 ICANS
If there is no clinical improvement within 24 to 72 hours, then re-evaluation for other contributing conditions should be done. Administration of IV Tocilizumab at 8 mg/kg (for participants weighing ≥30 kg, total dose should not exceed 800 mg) or alternative therapies per site practice in CRS management should be considered, and steroids should be administered concurrently and repeated as previously mentioned for CRS. Neurologist and other relevant clinical specialists should be involved whenever indicated. |

a Information for preparation and storage of SAR444245 is provided in the pharmacy manual  
Abbreviations: AE = Adverse event; ASTCT=American Society for Transplantation and Cellular Therapy; CRS= cytokine release syndrome; IV = Intravenous; NCI = National Cancer Institute.

### 6.5.4.6 Vascular Leak Syndrome (VLS)

Vascular leak syndrome is a disorder characterized by leakage of intravascular fluids into the extravascular space and can lead to generalized edema and multiple organ failure. This syndrome is observed in patients who demonstrate a state of generalized leaky capillaries following shock syndromes, low-flow states, ischemia-reperfusion injuries, toxemias, medications, or poisoning. In various human diseases, an increase in capillary permeability to proteins leads to the loss of protein-rich fluid from the intravascular to the interstitial space manifested by any of the following **clinical presentations: diffuse pitting edema, exudative serous cavity effusions, noncardiogenic pulmonary edema, hypotension, and, in some cases, hypovolemic, shock with multiple-organ failure.** Fluid management is the cornerstone of VLS management; it is a balance between maintaining the intravascular volume to ensure organ perfusion to prevent organ failure, while avoiding volume overload. The management of VLS according to severity grading is described in [Table 7](#). These guidelines are not comprehensive and the Investigator should exercise clinical judgment based on the symptoms and condition of the individual participant and refer to current guidelines to the topic ([29](#)).

**Table 7 - Guidelines for the management of Vascular Leak Syndrome (VLS)**

| Event severity
(NCI-CTCAE V5.0)   | Recommended SAR444245
dose modification and supportive care guidelines  |
|--|--|
| Mild
Grade 1
Asymptomatic   | No intervention required other than clinical monitoring.  |
| Moderate
Grade 2
Symptomatic; medical intervention indicated  | Delay SAR444245. Upon resolution of VLS or improvement to Grade 1, SAR444245a can be resumed at the reduced dose of █ μg/kg.
The initial strategy is to administer boluses of crystalloids with a goal of providing the minimum effective volume that optimizes blood pressure together with a fluid-restrictive strategy is advocated to limit interstitial fluid volume expansion.  |
| Severe or Life-threatening
Grade 3:
Severe symptoms; intervention indicated

Grade 4:
Life-threatening consequences; urgent intervention indicated | If Grade 3 or Grade 4 VLS, permanently discontinue SAR444245.
In participants with severe shock, blood pressure may be only partially responsive or refractory to IV crystalloid fluids.
Severe or persistent hypotension is to be managed by the administration of vasopressors. A trial of 25% albumin IV is an additional option, although its efficacy is limited to those with a severe capillary leak. In those who remain with refractory shock in the setting of low filling pressures, high molecular weight starches such as hetastarch (MW 450 kDa) and pentastarch (MW 264 kDa) may be effective in expanding the intravascular volume. Supportive care with invasive and noninvasive ventilation as well as renal replacement may be necessary in severe cases. When available, disease-specific therapy should be initiated as soon as possible to facilitate recovery. |
|  | During the recovery phase from severe capillary leak, the endothelial injury resolves and the capillary leak becomes less important, resulting in stabilization of blood pressure, at which time fluid overload symptoms and signs may predominate (eg, pulmonary edema, pleural effusions, acute respiratory distress syndrome, systemic edema, ascites). Volume removal with loop diuretics is the first-line therapy in these patients. In those with   |

| Event severity
(NCI-CTCAE V5.0) | Recommended SAR444245
dose modification and supportive care guidelines   |
|--|---|
|  | marginal blood pressure and fluid overload, the combination of loop diuretics and 25% albumin IV may facilitate volume removal. Patients with AKI refractory to diuretics will require renal replacement. |

a Information for preparation and storage of SAR444245 is provided in the pharmacy manual.

Abbreviations: AE = Adverse event; CTCAE = Common terminology criteria for adverse events; IV = Intravenous; NCI = National Cancer Institute.

## 6.6 CONTINUED ACCESS TO INTERVENTION AFTER THE END OF STUDY

Please refer to the master protocol.

## 6.7 TREATMENT OF OVERDOSE

Please refer to the master protocol for definition and treatment of SAR444245 overdose.

There is no specific antidote for overdose with pembrolizumab. No specific information is available on the treatment of overdose of pembrolizumab. In the event of overdose, the participant should be observed closely for signs of toxicity. Appropriate supportive treatment should be provided if clinically indicated.

## 6.8 CONCOMITANT THERAPY

Please refer to the master protocol.

## **7 DISCONTINUATION OF STUDY INTERVENTION AND PARTICIPANT DISCONTINUATION/WITHDRAWAL**

### **7.1 DISCONTINUATION OF STUDY INTERVENTION**

Please refer to the master protocol.

### **7.2 PARTICIPANT DISCONTINUATION/WITHDRAWAL FROM THE STUDY**

Please refer to the master protocol.

### **7.3 LOST TO FOLLOW UP**

Please refer to the master protocol.

## 8 STUDY ASSESSMENTS AND PROCEDURES

Please refer to the master protocol.

### 8.1 EFFICACY ASSESSMENTS

Please refer to the master protocol.

### 8.2 SAFETY ASSESSMENTS

#### 8.2.1 Physical examinations

Please refer to the master protocol.

#### 8.2.2 Vital signs

- Blood pressure and pulse measurements should be preceded by at least 5 minutes of rest for the participant in a quiet setting without distractions (eg, television, cell phones).
- Vital signs including temperature, pulse rate, respiratory rate, and blood pressure will be measured after 5 minutes rest.
- At Cycle 1 Day 1, vital signs after infusion initiation will be collected more intensively;
  - Vital signs will be measured at Pre-dose, 0.5 ( $\pm 0.25$ ), 1 ( $\pm 0.25$ ), 2 ( $\pm 0.5$ ), 4 ( $\pm 0.5$ ) hours after start of SAR444245 dose.
  - At Investigator's discretion, participants (not in the safety run-in) may have intensive vital sign monitoring (to be measured at Pre-dose, 0.5 ( $\pm 0.25$ ), 1 ( $\pm 0.25$ ), 2 ( $\pm 0.5$ ), 4 ( $\pm 0.5$ ), 8 ( $\pm 0.5$ ), 12 ( $\pm 1$ ), 16 ( $\pm 1$ ), 20 ( $\pm 1$ ), 24 ( $\pm 1$ ) hours after start of SAR444245 dose in an in-patient setting).
- **For the core phase participants:** from Cycle 2 to Cycle 4 study therapy will be administered for all patients in out-patient clinic with vital signs taken at baseline, at least 4 to 6 hours after the start of SAR444245 dosing, or for longer periods of time if clinically indicated.

